5.5.3 Labelling

Labels will be prepared in accordance with Good Manufacturing Practice (GMP) and local regulatory guidelines. The labels will fulfil GMP Annex 13 requirements for labelling. Label text will be translated into local language.

The label will include the following information:

- Study code
- Enrolment code
- Number of product
- Dosage form, route of administration, number of doses
- Visit no
- For clinical study use only
- Dosing directions
- Dr.....(to be filled in by hospital staff)
- Expiry date: dd-mm-yy
- Store at room temperature <30°C
- Keep out of reach of children
- AstraZeneca Pharmaceuticals,

5.5.4 Storage

All study drugs should be kept in a secure place under appropriate storage conditions, room temperature < 30°C.

5.6 Concomitant and post-study treatment(s)

Other medication, which is considered necessary for the subject's safety and well being, may be given at the discretion of the investigator and recorded in the appropriate sections of the Case Report Form. On enrolment into the study, patients should stop any current GERD/anti-reflux medication for at least 2 weeks.

Following completion of the study, patients will be treated at the discretion of the investigator.

5.7 Treatment compliance

The administration of all medication (including investigational products) should be recorded in the appropriate sections of the Case Report Form (CRF).

5.7.1 Accountability

The study drug provided for this study will be used only as directed in the study protocol.

Subject compliance with study drug dosing will be determined by tablet count. At Visit 2 and 3, 5, 6 (Visit 3, 5, 6 only for 8 weeks treatment regimen group) and unscheduled visit, the subject will be dispensed the study medication. The subject will be asked to bring all unused medication at the subsequent visit. The investigator, or delegate, will count and record the amounts of the remaining study drug in the CRF. The investigator, or delegate, will ask the subjects about discrepancies in the drug count or the study drug prescribed, and the explanation will be recorded in the CRF.

At Visit 7 or at premature withdrawal, the subjects will be asked to return all remaining investigational products dispensed at the prior visit, to the investigator. Study site personnel will account for all received study drugs and return all unused study drugs to AstraZeneca for destruction.

Documentation of amounts of study drugs delivered, returned and destroyed and how these procedures are carried out will be made.

5.8 Discontinuation of investigational product

Patients may be discontinued from investigational product (IP) in the following situations:

- Patient decision. The patient is at any time free to discontinue treatment, without prejudice to further treatment
- Adverse Event
- Severe non-compliance to study protocol
- Development of any study exclusion criteria

Patients with persisting symptoms after the 8 weeks treatment in 8 weeks treatment regimen group or 2 weeks treatment in 2 weeks treatment regimen group will be withdrawn from the study and treated according to the clinical routines.

5.8.1 Procedures for discontinuation of a subject from investigational product

A subject that decides to discontinue investigational product will always be asked about the reason(s) and the presence of any adverse events. Adverse events will be followed up (See Sections 6.4.3 and 6.4.4); diary cards, questionnaires and study drug should be returned by the subject. If possible, the subject should return for a clinic visit at the time of or soon after discontinuation of the study to have the following assessments made:

- SAEs and DAEs assessments
- Concomitant medication review
- GerdQ assessment
- Patient satisfaction assessment
- Drug accountability

5.9 Withdrawal from study

Subject will be withdrawn from study if discontinuation of investigational product.

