	Week -1	Week 0	Week 2	Week 8 ^b	
Inclusion & exclusion criteria	X	X			
Informed Consent	X				
Randomisation		X			
Medical history	X				
Demographic data	X				
Urine HCG ^c		X			
Physical examination	X				
Vital signs	X				
Laboratory measurement ^d	X				
Hp infection ^{d,e}	X				
Concomitant medication	X	X	X	X	
Drug dispensing		X	X ^b		
Drug accountability			X	X	
GerdQ assessment	X				
SAEs/ DAEs ^f assessment	X ^g →	X→	X→	X→	

^a Once informed consent given, baseline procedures may be completed within 1 week prior to treatment start.

^b Just for patients in 8 weeks treatment regimen group.

- ^c For women of child-bearing potential, a pregnancy test with a negative result must have been made before study.
- ^d Laboratory test results in the previous 2 weeks are acceptable, no need to repeat laboratory test at Visit 1.
- ^e Hp infection status diagnosed by ¹³C-urea breath test (UBT), rapid urease test or pathologic test.
- ^f Only SAEs and DAEs will be collected.
- ^g SAEs will be captured from time of signature of informed consent. DAEs will be captured from time of first dose of IP.

Table 2 Study Plan 2 (Visits in 24 weeks on-demand maintenance treatment/ follow-up period)

	24-week Maintenance treatment/ follow up			
	5 Week 8 ± 3d	6 Week 16 ± 3d	7 ^a Week 24 ± 3d	Unscheduled ^b
Concomitant medication	X	X	X	X
Drug dispensing	X ^c	X ^c		X
Drug accountability	X	X	X	X
GerdQ assessment	X	X	X	
Patient satisfaction	X	X	X	
SAEs/ DAEs ^d assessment	X→	X→	X	X

- ^a If a patient discontinues from the study prior to the Week 24 visit (study completion), every effort should be made to have the patient return for a clinic visit at the time of, or soon after discontinuation to complete all Final Visit procedures.
- ^b This includes all unscheduled visits carried out during maintenance treatment/ follow up period due to symptom recur and extra treatment needed. Total unscheduled visits will be compared between two treatment group.
- ^c Just for patients in 8 weeks treatment regimen group, only after the first relapse happened. If patients in CG group have symptom relapse at a scheduled visit, drugs will also be dispensed to them.
- ^d Only SAEs and DAEs will be collected.

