5.5.2 Doses and treatment regimens

Patients will be randomized into below two groups at the Visit 2.

8 weeks treatment regimen group:

Patients will receive 8 weeks esomeprazole 20 mg qd treatment, if symptom relieved (defined as no more than one day with mild symptoms of GERD during the previous 7 days), they will receive another 24 weeks on-demand maintenance treatment. The first drug dispensing during maintenance phase is the time of first relapse, which is defined as patients' symptom recur, go to consult investigators and need treatment in the opinion of investigator. The following on-demand drugs will be dispensed at Visit 5 and 6 if the first relapse happened before Visit 5. Patients will be instructed to "Take one tablet daily if needed for relief of your reflux symptoms for at least 3-5 days. Stop taking the tablets when your symptom is adequately controlled."

During 24 weeks on-demand maintenance treatment period, 14 tablets esomeprazole will be dispensed at each scheduled visit. If it is not enough before next scheduled visit, patients can

go to the study center to get extra drugs. If they do not have symptoms recur, and just come to get on-demand drugs, it is not considered as unscheduled visit.

2 weeks treatment regimen group:

Patients will receive 2 weeks esomeprazole 20 mg qd treatment, if symptom relieved, they will enter 24 weeks follow-up period. During the followed up period, if the patients' symptom recur and need treatment in the opinion of investigator, they will be given another 2-week esomeprazole 20 mg qd recurrent treatment. There is no limitation for the times of recurrent treatment in the 24-week follow up period.

Study medication should be taken once daily in the morning with a glass of water.

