In the 8 weeks treatment regimen group, to compare the symptom relief rate after 2 weeks and 8 weeks treatment	In the 8 weeks treatment regimen group, the symptom relief rate after 2 weeks and 8 weeks treatment (Symptoms relief are defined as no more than one day with mild symptoms of GERD during the previous 7 days). (ITT)	Summary statistics (number and percentage of patients in each category).
To compare the number of unscheduled hospital visit between the two different treatment regimen groups.	The number of unscheduled hospital visit in the two treatment regimen groups. (MITT and PP)	Descriptive statistics (number, mean, median, standard deviation, minimum and maximum). Treatment group comparison of unscheduled hospital visit, two sample t-test.
To measure patient satisfaction in the two different treatment regimen groups.	The proportion of patients satisfied (scores 1-4) or very satisfied (scores 1-2) in the two different treatment regimen groups after 8, 16 and 24 weeks on-demand maintenance treatment/ follow up. (MITT and PP)	Summary statistics (number and percentage of patients in each category). Treatment group comparison of proportion of patients satisfied and very satisfied, Fisher's Exact test.

Revised text:

Table 2 Efficacy objective and endpoints relating to objective

Objective	Summary variables for analysis (including timepoint and population)	Statistical analysis methods or presentation of data
Primary Objective	Primary variable	

Objective	Summary variables for analysis (including timepoint and population)	Statistical analysis methods or presentation of data
To compare the symptom control rate between 8 weeks esomeprazole treatment regimen group and 2 weeks esomeprazole treatment regimen group in co-diagnosed NERD and chronic gastritis patients, as evaluated by GerdQ after 24 weeks maintenance treatment/follow up.	The symptom control rate in 8 weeks treatment regimen group, compared with 2 weeks treatment regimen group after 24 weeks on-demand maintenance treatment/ follow up. Controlled patients are defined as patients with all items ≤ 1 in A and C category of GerdQ. (MITT and MITT-PP)	Summary statistics (number and percentage of patients in each category). Treatment group comparison of proportion of patients controlled, Fisher's exact test.
Secondary Objective	Secondary variable	

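### Section 5.9 ends follow-up when study drug stops, so these patients have no Week 24 GerdQ for the primary comparison

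*Protocol*

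**What the plan says.** Section 5.9 is a single unconditional sentence: "Subject will be withdrawn from study if discontinuation of investigational product". Section 5.8 introduces the reasons with "Patients may be discontinued from investigational product (IP) in the following situations" and lists the patient's own choice, an adverse event, severe non-compliance, and "Development of any study exclusion criteria". It separately withdraws "Patients with persisting symptoms after the 8 weeks treatment in 8 weeks treatment regimen group or 2 weeks treatment in 2 weeks treatment regimen group".

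Two places ask for an assessment when a patient stops. Section 5.8.1 says "If possible, the subject should return for a clinic visit at the time of or soon after discontinuation of the study" and includes GerdQ among the assessments. Table 2, footnote a (section 3.1) says "every effort should be made to have the patient return for a clinic visit at the time of, or soon after discontinuation", so that the Final Visit procedures are done then. Neither asks for anything further at Week 24.

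The primary variable, in the section 6.3.1 table as revised by Amendment 1, is control after 24 weeks: "Controlled patients are defined as patients with all items ≤ 1 in A and C category of GerdQ". Section 12.1 analyses efficacy by randomised treatment. Revised section 12.1.1 makes MITT, the patients relieved by their initial treatment, the primary population.

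In the 24-week phase (section 5.5.2), the 2-week group receives drug only for a recurrence that the investigator judges to need treatment. The 8-week group receives none until first relapse and is then told "Stop taking the tablets when your symptom is adequately controlled".

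**The concern.** Stopping drug and leaving the study are different events, and section 5.9 merges them. A relieved patient who later discontinues remains in MITT, but the protocol has no provision for observing the primary outcome. A comparison by randomised arm then depends on patients selected by something that happened after randomisation.

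Some of the section 5.8 reasons could be related to symptom control. The patient's own choice, in an open-label trial, may reflect dissatisfaction with the regimen. A new exclusion criterion could be visible reflux esophagitis (section 4.2, criterion 4). Non-compliance could involve self-medication, which GerdQ category C asks about and which therefore enters the definition of control. The arms also hold drug at different times, so the rule may apply unequally between them.

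The rule is also hard to apply in the phase that produces the endpoint, because patients are often off drug by design. Amendment 1's reason for the section 5.5.2 change reports that some 8-week patients used up their tablets and came back only when symptoms recurred. The protocol does not say whether such a gap is discontinuation, so centres could read section 5.9 differently.

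**Working it through.** **Inputs (section 12.3).** Control 86% (8-week) v 66% (2-week); 85 evaluable per arm; two-sided 5% Fisher test; 70% response; 20% drop-off; about 300 randomised. Allocation is equal (section 5.2.1).

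**1. The plan's own figures.** Full binomial enumeration of the Fisher test at 85 per arm gives power of 83.8%, consistent with the stated figure of over 80%. The inflation is 170 / (0.70 × 0.80) = 303.6, consistent with about 300. Both reproduce.

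**2. Patients who could lack a Week 24 value.** Relieved patients: 300 × 0.70 = 210, or 105 per arm. At 20% drop-off, 105 × 0.20 = 21 per arm are lost and 84 are observed. The 20% covers every cause, including losses that no change to section 5.9 could prevent, and has no stated timing. Drop-outs before the relief assessment would not be in MITT. So 21 per arm is a ceiling on loss due to this rule.

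**3. Effect on the difference.** The protocol does not give control rates among lost patients, so they are assumed here. Let w8 and w2 be those rates, with patients who have a Week 24 value at 86% v 66%.

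- MITT rate, 8-week arm = 0.80 × 0.86 + 0.20 × w8
- MITT rate, 2-week arm = 0.80 × 0.66 + 0.20 × w2
- Overstatement by observed cases = 0.20 − (difference in MITT rates) = 0.20 × [0.20 − (w8 − w2)]

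| w8 | w2 | MITT rates | Difference (points) | Overstatement (points) |
|---|---|---|---|---|
| 86% | 66% | 86.0% v 66.0% | 20.0 | 0 |
| 0% | 0% | 68.8% v 52.8% | 16.0 | +4.0 |
| 50% | 50% | 78.8% v 62.8% | 16.0 | +4.0 |
| 0% | 66% | 68.8% v 66.0% | 2.8 | +17.2 |
| 86% | 0% | 86.0% v 52.8% | 33.2 | −13.2 |

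With equal loss in both arms, any common rate among lost patients gives a 4-point overstatement. Larger errors in either direction need rates that differ by arm, for which the protocol gives no basis.

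**4. The same scenario in terms of power.** If all 21 per arm counted as not controlled, exact Fisher power at 105 per arm with 68.8% v 52.8% is 62.0%, against 83.8% planned.

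**5. Can the early GerdQ replace Week 24?** The questionnaire (Appendix C) asks about the past seven days. A reading at, for example, Week 6 describes Week 6. Table 2 places the Week 24 visit within ± 3 days. The two measure different things.

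**The case against.** The strongest reply is that the rule may cost little. Section 5.8 says that patients may be discontinued, and symptom recurrence in the 24-week phase is not a listed reason. Recurrence is treated inside the study, with on-demand tablets in one arm and repeat courses in the other. Patients not relieved initially are outside MITT by definition. Section 5.1 bars other PPIs and H2RAs but does not say that using one ends study drug. Completing a course, or stopping tablets when controlled as instructed, follows the regimen and is not a section 5.8 event. A GerdQ is sought at discontinuation, and missing-data rules may be in the SAP.

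Much of this stands, and it rules out several stronger readings:

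- A reader might infer that the patients lost are those most likely to be uncontrolled, so that the comparison is biased. The listed reasons make a link possible but do not establish it, and the direction of any bias is unknown.
- A reader might quote worst-case limits of −4 points (0.688 − 0.728) to +36 points (0.888 − 0.528). These require every lost patient to be controlled in one arm and none in the other. Any trial with 20% missing has such limits, and they do not measure the effect of section 5.9.
- A reader might infer from footnote a that an early GerdQ will be analysed as the Week 24 outcome. The footnote asks only that Final Visit procedures be completed and is silent on analysis.

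The reply does not remove the main point. An SAP can choose how to treat missing values, but it cannot supply Week 24 outcomes that were not collected.

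**Conclusion.** The point holds as an avoidable gap in outcome collection. Followed as written, section 5.9 leaves every MITT patient who discontinues drug without a Week 24 GerdQ, for post-randomisation reasons, in an open-label comparison by randomised treatment. The loss may be informative and unequal between arms, but the protocol does not allow its sign or size to be derived.

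For scale, at most about 21 of 105 relieved patients per arm would be affected, taking the whole all-cause drop-off as the ceiling. If none of them were controlled, the planned 20-point difference would be 16 points. If they resembled the patients who have Week 24 values, there would be no bias. These figures assume equal loss in both arms and assumed control rates among those lost. The uncertainty about what counts as discontinuation in the 24-week phase is a separate point of clarity and does not itself show lost outcomes.

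**What to change.** Amend section 5.9 so that stopping study drug and leaving the study are separate events. A patient who stops drug stays in follow-up for GerdQ, satisfaction and visit counts at the existing Week 8, 16 and 24 time points, unless consent is withdrawn. Record the GerdQ taken at early discontinuation as its own visit, not as Week 24. Reconcile section 5.9 with sections 5.8.1 and 5.5.2 and Table 2, footnote a, and state what counts as discontinuation of investigational product for a patient who is off drug by design.

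This changes data collection only and proposes no change to dosing or to the reasons for stopping treatment. The cost is amendment wording and a few extra contacts on the existing schedule. Some outcomes will be measured after other treatment, which is acceptable in a comparison of regimens but should be recorded. Handling of values still missing is left to the SAP.

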6. COLLECTION OF STUDY VARIABLES

6.1 Recording of data

The investigator will ensure that data are recorded on the paper Case Report Forms as specified in the study protocol and in accordance with the instructions provided.

The investigator ensures the accuracy, completeness, legibility and timeliness of the data recorded and of the provision of answers to data queries according to the Clinical Study Agreement. The investigator will sign the completed paper Case Report Forms. A copy of the completed paper Case Report Forms will be archived at the study site.

6.2 Data collection and enrolment

At enrolment, below data will be collected:

- Age, sex and race
- Standard/significant medical and surgical history
- Physical examination and vital signs
- Blood sample for standard clinical chemistry and haematology, urine sample for urinalysis
 - Clinical chemistry: AST, ALT, creatinine, BUN
 - Haematology: Haemoglobin, leukocyte and thrombocyte counts
 - Urinalysis: pH, protein, erythrocyte, leukocyte and additional urine analyses.
- Pregnancy test
- GerdQ score
- Hp infection status (diagnosed with ¹³C-urea breath test (UBT), rapid urease test or pathologic test)
- Concomitant medication

6.2.1 Follow-up procedures

Refer to Study Plan ([Table 1](#) and [Table 2](#)) what procedures will be made at each specific follow-up visit.

6.3 Efficacy

The appropriateness of the efficacy measurements and variables in this study are addressed in Section [3.2](#).

6.3.1 Summary of efficacy objectives and variables

Table 3 shows how the efficacy endpoint of this study relates to the study objective.

Table 3 Efficacy objective and endpoints relating to objective

Objective	Summary variables for analysis (including timepoint and population)	Statistical analysis methods or presentation of data
Primary Objective	Primary variable	
To compare the symptom control rate between 8 weeks esomeprazole treatment regimen group and 2 weeks esomeprazole treatment regimen group in co-diagnosed NERD and chronic gastritis patients, as evaluated by GerdQ after 24 weeks maintenance treatment/follow up.	The symptom control rate in 8 weeks treatment regimen group, compared with 2 weeks treatment regimen group after 24 weeks on-demand maintenance treatment/ follow up. Controlled patients are defined as patients with all items ≤ 1 in A and C category of GerdQ. (ITT, MITT and PP)	Summary statistics (number and percentage of patients in each category). Treatment group comparison of proportion of patients controlled, Fisher's exact test.
Secondary Objective	Secondary variable	
To assess time to first relapse.	Time to first relapse, defined as the time to the patients first come to see the investigator because of symptom recur and need for treatment after 8 weeks or 2 weeks treatment in the two treatment regimen groups. (MITT and PP)	Median and percentiles of time to relapse, if appropriate. Treatment group comparison using Log-Rank test.
To assess symptom control rate after 8 /16 weeks visits in 24 weeks maintenance treatment/follow up period, as evaluated by GerdQ.	The symptom control rate after 8 and 16 weeks on-demand maintenance treatment/ follow up in the two different treatment regimen groups. Controlled patients are defined as patients with all items ≤ 1 in A and C category of GerdQ. (ITT, MITT and PP)	Summary statistics (number and percentage of patients in each category). Treatment group comparison of proportion of patients controlled, Fisher's exact test.

Objective	Summary variables for analysis (including timepoint and population)	Statistical analysis methods or presentation of data
To assess the symptom relief rate after 8 weeks or 2 weeks esomeprazole treatment in the two different treatment regimen groups.	The symptom relief rate after 8 weeks or 2 weeks treatment in the two treatment regimen groups (Symptoms relief are defined as no more than one day with mild symptoms of GERD during the previous 7 days). (ITT)	Summary statistics (number and percentage of patients in each category).
In the 8 weeks treatment regimen group, to compare the symptom relief rate after 2 weeks and 8 weeks treatment	In the 8 weeks treatment regimen group, the symptom relief rate after 2 weeks and 8 weeks treatment (Symptoms relief are defined as no more than one day with mild symptoms of GERD during the previous 7 days). (ITT)	Summary statistics (number and percentage of patients in each category).
To compare the number of unscheduled hospital visit between the two different treatment regimen groups.	The number of unscheduled hospital visit in the two treatment regimen groups. (MITT and PP)	Descriptive statistics (number, mean, median, standard deviation, minimum and maximum). Treatment group comparison of unscheduled hospital visit, two sample t-test.
To measure patient satisfaction in the two different treatment regimen groups.	The proportion of patients satisfied (scores 1-4) or very satisfied (scores 1-2) in the two different treatment regimen groups after 8, 16 and 24 weeks on-demand maintenance treatment/ follow up. (MITT and PP)	Summary statistics (number and percentage of patients in each category). Treatment group comparison of proportion of patients satisfied and very satisfied, Fisher's Exact test.

